### **Final visit/End of observation period**

The final data collection (last visit) is at the end of study (regular end of study or after further follow-up for patients with BMD decrease or osteoporosis) or at discontinuation of Yselyt® therapy for patients without BMD decrease or osteoporosis (whatever is earlier). At this final observation point, the patient's condition and a treatment assessment will be documented as a follow-up visit with additional information on:

- Regular end of observation, or
- End of observation after further follow-up for patients who discontinued Yselyt® treatment but had a BMD decrease or osteoporosis (see section above) during the study, or
- Discontinuation of follow-up with the reason for discontinuation (e.g., end of therapy with Yselyt® and no BMD decrease or osteoporosis).

**Table 1 Estimated schedule for the Yselty® PASS**

	First Visit (Enrolment)	Baseline (Yselty® Treatment Start) 	Observation Time Points  (Months Since Yselty® Treatment Start)			
			12	24	36	48
Assessment of inclusion/exclusion criteria	X	–	–	–	–	–
Date of signed informed consent	X	–	–	–	–	–
Date of first Yselty® dose	–	X	–	–	–	–
Year of birth	X	–	–	–	–	–
Sex	X	–	–	–	–	–
Height/weight	X	–	–	–	–	–
Yselty® dosing regimen (100 mg without ABT, 100 mg with ABT, or 200 mg with ABT)	X	–	X	X	X	X
Medical history	X	–	–	–	–	–
Concomitant diseases	X	X				
Alcohol/nicotine/drug/stimulant consumption	X	–	X	X	X	X
Relevant prior medication	X	–	–	–	–	–
Relevant concomitant medication	X	–	X	X	X	X
BMD assessment, including absolute density values, z-score/t-score values, DXA scan date, anatomic site of DXA scan, machine type, imaging parameters, reference population used (if available)	X	–	X	X	X	X
Clinical evaluation (including weight, blood pressure, clinical assessment of fibroid)	X	–	X	X	X	X
Change in Yselty® dosing regimen, reasons for change	–	–	X	X	X	X
Reported adherence to prescribed treatment	–	–	X	X	X	X
Laboratory values  and date of laboratory assessment (if available)	X	–	X	X	X	X
Liver enzyme elevation events 	X	–	X	X	X	X
Bone fracture events 	X	–	X	X	X	X
Events of uterine endometrial adenocarcinoma and mammary gland adenocarcinoma	X	–	X	X	X	X

	First Visit (Enrolment)	Baseline (Yselty® Treatment Start) 	Observation Time Points  (Months Since Yselty® Treatment Start)			
			12	24	36	48
Mood disorder events 	X	–	X	X	X	X
Cardiac disorder events suggestive of potential QT interval prolongation	X	–	X	X	X	X
ECG findings indicative of QT interval prolongation, according to the physician's information	X	–	X	X	X	X
RMP targeted follow-up questionnaires on uterine endometrial and mammary gland adenocarcinoma, QT interval prolongation, exposure in pregnancy/pregnancy outcome, cases of elevated liver enzymes 			X	X	X	X
AEs, SAEs, ADRs, SADRs, special situations 	X	–	X	X	X	X
Premature discontinuation, including reasons 	–	–	X	X	X	X

1 Date of first visit (enrolment) and date of first Yselty® dose (baseline) may be the same, or the date of first Yselty® dose may be up to 3 months prior to first visit. For patients with first Yselty® treatment before enrolment, baseline data can be documented retrospectively at enrolment.

2 This is the expected visit schedule, however, visits are to be performed as per routine practice. Additional visits can also be recorded. In case the observational period per country is prolonged, data collection will be prolonged as well.

3 Laboratory values include 25-hydroxy vitamin D, if available, and liver enzyme levels or values indicative of liver injury such as ALT, AST, bilirubin, GGT, and ALP, if available.

4 A list of MedDRA terms for hepatic events is available as a stand-alone document (see section 15.1) and will be further specified in the SAP.

5 Including events of osteoporosis or fractures suspected to be due to osteoporosis; all suspected osteoporotic fractures (minimal- or non-traumatic) of long bones or spine where the physicians suspect an osteoporotic cause of the fracture.

6 Including events of mood swings, affect lability, emotional disorder, irritability, mood altered, anxiety, bipolar disorder, mania, depression, depressed mood.

7 The RMP (see section 15.1) contains a targeted follow-up questionnaire for events indicative of uterine endometrial and mammary gland adenocarcinoma, QT interval prolongation, exposure in pregnancy/pregnancy outcome, and cases of elevated liver enzymes. Physicians who report an event indicative of these events will be sent the appropriate targeted follow-up questionnaire.

8 In case of discontinuation, AEs, SAEs, ADRs, SADRs, and special situations have to be documented as outlined in section 11.3.

9 Special situations include drug interactions, medication abuse, medication misuse, medication overdose, medication errors, unexpected therapeutic or clinical benefit from product use, pregnancy or lactation exposure with the product, lack of efficacy, off-label use, and occupational exposure (see section 11.4).

10 Physicians should continue to document BMD measurements during the extended follow-up period for patients who experienced BMD decrease or osteoporosis during the study. Management of AE/ADR occurring after treatment discontinuation will be managed in accordance with section 11.3.

ABT=add-back therapy; ADR=adverse drug reaction; AE=adverse event; ALP=alkaline phosphatase; ALT=alanine aminotransferase; AST=aspartate aminotransferase; BMD=bone mineral density; DXA= Dual-energy X-ray absorptiometry; ECG=electrocardiogram; GGT=gamma-glutamyl transferase; MedDRA= Medical Dictionary of Regulatory Activities; RMP=Risk Management Plan; SADR=serious adverse drug reaction; SAE=serious adverse event; SAP=Statistical Analysis Plan.

## **9.3 Variables**

### **9.3.1 Demographic Data and Other Baseline Characteristics**

The following data will be recorded at first visit (enrolment):

- Date of patient consent
- Year of birth
- Sex
- Height, body weight
- Yselty® dosing regimen

The following data will be recorded at Yselty® treatment start (baseline):

- Date of first Yselty® dose

### **9.3.2 Comorbidities (Medical History, Concomitant Diseases)**

Comorbidities are any relevant medical findings that were present before start of therapy with Yselty®, independent of whether or not they are still present. They have to be documented in the Medical History/Concomitant Diseases section of the eCRF at the enrolment visit. Specific medical history will be collected on initial diagnosis, history of disease, history of an indication for surgical treatment of fibroids, as well as in the categories of:

- Previous fracture
- Mood disorders, including family history
- Hepatic disorders
- Cardiac disorders
- Malignant carcinoma
- Other relevant risk factors for osteoporosis or bone loss (including alcohol abuse, smoking, obesity, strong family history of osteoporosis, type I diabetes mellitus, rheumatoid arthritis, Vitamin D absorption disorders, Paget disease, osteogenesis imperfecta in adults, chronic kidney disease, untreated long-standing hyperthyroidism, chronic malnutrition, or malabsorption and chronic liver disease and long-term use of systemic steroids)

For any comorbidity, the diagnosis and if the disease is still ongoing at time of enrolment visit have to be documented.

---

 Date of first visit (enrolment) and date of first Yselty® dose (baseline) may be the same, or the date of first Yselty® dose may be up to 3 months prior to the first visit.

A clinical evaluation, including body weight, blood pressure, and clinical assessment of the fibroid, will be performed at enrolment visit and at follow-up visits, as per routine clinical practice.

### **9.3.3 Prior and Concomitant Medication**

Medication taken before study start (initiated and stopped before study start) are defined as prior medications. All medication taken in addition to the prescribed Yselty® dosing regimen for any indication (either initiated before study start or during the study) are defined as concomitant medications.

Information on prior treatment with ABT, prior treatments for fibroids (labelled and off-label), previous GnRH-agonist treatment, and previous systemic treatment (glucocorticoids, aromatase inhibitors, thiazolinediones, thyroxine, drugs targeting the immune system (such as calcineurin inhibitors and antiretroviral drugs), selective serotonin reuptake inhibitor anticonvulsants, loop diuretics, heparin, and proton pump inhibitors) is to be collected as part of the enrolment data collection. Additionally, all relevant concomitant medication taken at enrolment and during the study will be recorded. Relevant concomitant medication includes anything influencing BMD loss (list defined for previous systemic treatment). Medications which may impact on liver enzyme increase or QT prolongation will be specified in the SAP.

Information on medication (including changes) will be collected in the categories stated below:

- Trade name or international non-proprietary name
- Start date (at least year)
- Stop date or “continued”
- Daily dose, if applicable
- Indication (prespecified categories: treatment of concomitant disease/treatment of AE/other)

### **9.3.4 Exposure/Treatment**

Information to be documented on Yselty® exposure/treatment includes:

- Start date
- Stop date (if applicable)
- Dosing regimen (200 mg with ABT, 200 mg without ABT, 100 mg with ABT, 100 mg without ABT)

---

 Exposure/treatment variables will inform on the exploratory endpoint assessing the proportion of patients starting each Yselty® dosing regimen, time spent on each dosing regimen, and changes in dosing regimens.

- Reason for interruption or premature discontinuation of Yselty® treatment (AE, withdrawal of consent, lost to follow-up, treatment with Yselty® discontinued permanently [pregnancy, onset of menopause], administrative problems, death, other), if applicable
- Reason for interruption or premature discontinuation of ABT (AE, withdrawal of consent, lost to follow-up, treatment with ABT discontinued permanently, administrative problems, death, other), if applicable
- Reason for dosing regimen change, if applicable

### **9.3.5 Variables to Assess the Primary Endpoint**

The variables for the primary endpoint **I**. are:

- BMD z-score measured in lumbar spine, total hip or femoral neck
- Date of DXA scan, if performed
- Anatomic site of DXA scan, machine type, imaging parameters of DXA scan, and reference population used, if available

### **9.3.6 Variables to Assess the Exploratory Endpoints**

The variables for the exploratory endpoints are:

- For objective **II.a**:
  - Osteoporosis diagnoses
  - Bone fracture events (long bones, spine)
  - For fractures, the probability of an osteoporotic cause of the fracture judged by the physician
  - Laboratory values of 25-hydroxy vitamin D, if available
- For objective **II.b**:
  - Laboratory values of liver enzyme levels or values indicative of liver injury such as alanine aminotransferase (ALT), aspartate aminotransferase (AST), bilirubin, gamma-glutamyl transferase (GGT), and alkaline phosphatase (ALP), if available
  - Date of laboratory assessment of liver enzyme levels, if performed
  - Elevated liver enzyme events
  - Events indicative of liver injury
- For objective **II.c**:
  - Mood disorder events of mood swings, affect lability, emotional disorder, irritability, mood altered, anxiety, bipolar disorder, mania, depression, depressed mood

- For objective **II.d**:
  - Uterine endometrial adenocarcinoma events
  - Mammary gland adenocarcinoma events
- For objective **II.e**:
  - Yselty® dosing regimen and changes in dosing regimens (see section 9.3.4)
- For objective **II.f**:
  - Reported patient adherence to prescribed treatment, including use of ABT
- For objective **II.g**:
  - Cardiac disorder events (ventricular arrhythmias [e.g., ventricular tachycardia and ventricular fibrillation, flutter, torsade de points], cardiac arrest, and sudden cardiac death) suggestive of potential QT interval prolongation
  - ECG findings indicative of QT interval prolongation, according to the physician's information
- For objective **II.h**:
  - DXA scan in defined time periods; Yes/No (see section 9.1.2)
  - DXA scan prior to treatment initiation in patients with risk factors for fractures, osteoporosis, or bone loss; Yes/No
  - Prescription of 200 mg Yselty® without concomitant ABT in defined time periods; Yes/No (see section 9.1.2)
- For objective **II.i**:
  - ADRs
  - SADR
- For objective **II.j**:
 

For patients with multiple DXA scans (at baseline and/or follow-up[s]):

  - BMD z-score and BMD t-score measured in lumbar spine, total hip, or femoral neck
  - Absolute value of density (g/cm^2)
  - Date of DXA scan, if performed
  - Anatomic site of DXA scan, machine type, imaging parameters of DXA scan, and reference population used, if available

### **9.3.7 Other Variables**

Other variables to be collected include:

- Alcohol/nicotine/drug/stimulant consumption
- AEs, SAEs, ADRs, SADR, special situations
- Risk Management Plan (RMP) targeted follow-up questionnaires (see section 9.4)

### **9.4 Data Sources**

The physician is requested to collect historical data (demographic and clinical characteristics) by reviewing the patient medical records, if available, by interviewing the patient, or during the clinical examination. Likewise, the physician collects treatment-related data during visits that take place in routine clinical practice.

In accordance with the RMP, targeted follow-up questionnaires will be used to collect information on:

- Uterine endometrial and mammary gland adenocarcinoma
- QT interval prolongation
- Exposure in pregnancy/pregnancy outcome
- Cases of elevated liver enzymes

Physicians who report an event indicative of these events will be sent the respective targeted follow-up questionnaire.

### **9.5 Study Size**

Approximately 1,000 women of reproductive age with documented uterine fibroids and symptoms such as HMB being treated with Yselyt® long-term, according to the SmPC. This is a multinational study in 5 European countries (Germany, Italy, Spain, Poland and UK), whereas the selection and sequence of countries may change depending on the launch dates of Yselyt®. The number of study sites will vary per country, dependent on use of Yselyt®.

This is a descriptive study and is not intended to test a formal hypothesis. The sample size is based on feasibility and practical considerations rather than statistical. Sample size considerations are based on the primary endpoint, BMD z-score, which compares bone mineral density with a reference population of the same age and sex. The BMD z-score will

---

 Special situations include drug interactions, medication abuse, medication misuse, medication overdose, medication errors, unexpected therapeutic or clinical benefit from product use, pregnancy or lactation exposure with the product, lack of efficacy, off-label use, and occupational exposure (see section 11.4).

be measured at 3 sites for each patient, i.e., lumbar spine, total hip, and femoral neck and the lowest individual value is used to estimate the population proportion.

A single-group design was used to obtain a 2-sided 95% confidence interval (CI) for a single proportion. Given the standard normal distribution of BMD z-scores (z-distribution), the expected sample proportion of values < -2 (cutoff for low bone density) is assumed to be 2.5%, which corresponds to the lower 2.5% quantile of the z-distribution. With an effective sample size of 800 (assuming 20% dropout), the CI width at 12 months of follow-up is 2.2% and the expected precision of the proportion is 2.5%±1.1% (see Table 2). Assuming a further 20% yearly dropout rate, at 24 months of follow-up, the effective sample size is estimated to be 640 patients with a CI width of 2.4% and an expected precision of the proportion of 2.5%±1.2%. At 36 months of follow-up, the effective sample size is estimated to be 512 patients with a CI width of 2.8% and an expected precision of the proportion of 2.5%±1.4%. At 48 months of follow-up, the effective sample size is estimated to be 409 patients with a CI width of 3.0% and an expected precision of the proportion of 2.5%±1.5%.

**Table 2 Precision and width of the confidence intervals for the estimated sample sizes at 1, 2, 3, and 4 years of follow-up**

Follow-up	Effective sample size (20% annual dropout)	Expected precision (half width of CI)	95% CI
At enrolment	1,000		
At 12 months	800	±1.10%	0.014 – 0.036
At 24 months	640	±1.20%	0.013 – 0.037
At 36 months	512	±1.35%	0.011 – 0.039
At 48 months	409	±1.50%	0.010 – 0.040

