## 6 Milestones

Milestone	Planned date
Start of data collection (FPFV)	Q1/Q2 2026
End of data collection (LPLV)	Q3/Q4 2029 The scheduled study duration per country includes a patient recruitment phase of up to 18 months and an individual prospective observational period for as long as feasible within the scheduled study timeframe. In case the observational period per country is prolonged, data collection will be prolonged as well.
Progress reports 	Progress reports related to the state of PASS recruitment will be part of every PSUR. The PSUR will be submitted as per the EURD list requirements.
Interim report	First interim report is expected in Q3/Q4 2028. Further interim analyses will be provided every two years unless the final report is delivered until Q4 2029.
Registration in the EU PAS register	Before start of data collection.
Final report of study results	December 2030 One year after end of data collection.

 Only if agreed with authorities.

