## 8 Research Question and Objectives

Data in patients taking Yselty® in the real-world setting and for more than 1 year is needed to better understand certain safety parameters associated with long-term use. The overall study aim is to assess the long-term safety of Yselty® when used in real life clinical practice.

The primary objective is:

- **I.** To evaluate routinely collected data on long-term safety (>12 months) in relation to BMD with use of Yselty® 200 mg (with ABT) and 100 mg (with and without ABT) dosing regimens.

The exploratory objectives are:

- **II.a** To evaluate the incidence of osteoporosis or fractures suspected to be due to osteoporosis
- **II.b** To evaluate liver enzyme levels above the upper limit of normal and correlated events collected as part of clinical practice
- **II.c** To evaluate any routinely collected clinical data on mood disorders
- **II.d** To evaluate the incidence of uterine endometrial and mammary gland adenocarcinoma
- **II.e** To describe treatment patterns for Yselty® dosing regimens with and without ABT
- **II.f** To evaluate patient adherence to Yselty® treatment
- **II.g** To evaluate any routinely collected clinical data on cardiac disorders indicative for QT interval prolongation
- **II.h** To assess if physicians who prescribe Yselty® follow the summary of product characteristics (SmPC) recommendations including performance of annual dual-energy X-ray absorptiometry (DXA) scans and adherence to the requirement of not prescribing the Yselty® 200 mg regimen without concomitant ABT
- **II.i** To evaluate the incidence of adverse drug reactions (ADRs), serious adverse drug reactions (SADRs) and pregnancies (including pregnancy follow-up)
- **II.j** To evaluate BMD change in patients with routinely collected DXA scans at multiple timepoints to assess mean change of BMD z- and t-scores from baseline or 12-month assessment during long-term (>12 months) use of Yselty®.

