  - Incidence rate of adverse events regarding electrocardiogram (ECG) findings indicative of QT interval prolongation, according to the physician's information
- For objective **II.h**:
  - Frequency of use of DXA scans in defined time periods:
    - Among patients with >1-year treatment, the number and proportion of Yselyt® users who received at least 1 DXA scan between 10 months until 14 months
    - Among patients with >2-year treatment, the number and proportion of Yselyt® users who received at least 2 DXA scans between 10 months until 26 months
    - Among patients with >3-year treatment, the number and proportion of Yselyt® users who received at least 3 DXA scans between 10 months until 38 months
    - Among patients with ≥4-year treatment, the number and proportion of Yselyt® users who received at least 4 DXA scans between 10 months until end of study
  - Frequency of DXA scans prior to treatment initiation in patients at high risk for osteoporosis or bone loss

---

 Additional analyses on ADRs will be performed.

 The RMP (see 15.1) contains targeted follow-up questionnaires for these events. Physicians who report these events will be asked to fill the corresponding targeted follow-up questionnaire.

 The RMP (see 15.1) contains targeted follow-up questionnaires for these events. Physicians who report these events will be asked to fill the corresponding targeted follow-up questionnaire.

 High risk patients will be identified by their treating physician as described in section 9.2.1.

- Number and proportion of patients who received Yselty® at a dose of 200 mg for more than 6 months without concomitant prescriptions for ABT at suitable time periods (e.g., 3-month intervals)
- For objective **II.i**:
  - Incidence rate of ADRs
  - Incidence rate of SADR
- For objective **II.j**:
  - Mean absolute and relative change in density (g/cm^2) and absolute value and relative change of BMD z-score and t-score from baseline (for patients with baseline DXA scan as per routine clinical practice – per SmPC only recommended for patients at high risk for osteoporosis or bone loss)

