#### **9.7.3.3 Analysis of Primary Endpoint**

The primary objective will only be assessed in users with the long-term treatment (>12 months) and where z-scores of lumbar spine, total hip, or femoral neck are available. For rates of events of BMD z-scores below the age-related threshold of -2 standard deviations, the number and percentage of patients with these events will be provided including 95% CIs.

The aggregated number, frequency of DXA scans, anatomic site of DXA scan, machine type, and imaging parameters of DXA scans during the observational period will be analysed by descriptive statistics. If results of DXA scans can be interpreted in a categorised way, shift tables for the change from baseline, will be provided, where available. If images of the DXA scans can be provided by the doctors, they will be reviewed by 1 independent expert for their suitability and included in an additional sensitivity analysis.

Sensitivity analyses using different criteria (e.g., machine type) to select DXA scans that ensure their comparability will be performed to evaluate the primary endpoint if the sample size allows (e.g., if more than 30 patients remain after selection of suitable cases) and will be further detailed in the SAP.

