## **9.9 Limitations of the Research Methods**

Possible limitations of the study are based on the observational design and the fact of voluntary participation of physicians and patients. Physicians and patients who voluntarily agree to participate in this study might differ from those who do not agree. Consecutive enrolment should avoid any selection bias and increase the likelihood of representativeness.

Although the study aims to include participants from a variety of geographic regions, there may be local limitations that reduce the representativeness of patients recruited, such as

patient access to recruiting physicians (including differences in patient profile in specialized, recruiting sites vs local general practice), Yselty® availability and reimbursement, and decisions relating to local standard of care.

The main objective depends on two factors that are crucial but beyond the control of the study: First, the overall uptake of Yselty® and the proportion of patients treated beyond 12 months. Second, the extent to which doctors perform DXA scans after 1 year (as recommended in the SmPC) as part of their routine care. Depending on the country, this could be either facilitated or hindered by the reimbursement status of DXA scans.

BMD measurements, the primary objective, have a good reproducibility under highly controlled conditions, but such conditions do not generally apply in clinical practice. Many factors could affect the accuracy of BMD testing, including inter-machine variance as well as the experience of the operator. In addition, a high rate of missing BMD measurements at week 24 and week 52 due to study discontinuations was observed in the two pivotal studies [11]. This indicates that BMD assessment may become difficult due to the low number of observations recorded, especially for long-term users which are of special interest in this study. When interpreting the proportion of patients with z-scores below -2 standard deviations indicating loss of bone density, it should be kept in consideration that normalisation of z-scores is usually based on BMD measurements for a single bone. If multiple measurements have been taken in a patient, the likelihood of results being below threshold increases with the number of bone sites examined for each patient.

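### Table 2 counts dropout but not the study calendar: 409 patients at 48 months cannot be reached under the stated milestones, and 512 at 36 months is probably a partial cohort

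*Protocol*

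**What the plan says.** Section 9.5 starts from "At enrolment 1,000" (Table 2) and applies a 20% loss in each year. The first step reads "With an effective sample size of 800 (assuming 20% dropout), the CI width at 12 months of follow-up is 2.2" per cent. The same rule gives 640 at 24 months, 512 at 36 months and, in the last step, "At 48 months of follow-up, the effective sample size is estimated to be 409 patients with a CI width of 3.0" per cent. Table 2 shows half-widths of 1.10, 1.20, 1.35 and 1.50 percentage points around an expected proportion of 2.5%.

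Section 6 gives the calendar. First patient first visit is Q1/Q2 2026. The entry for the end of data collection begins "Q3/Q4 2029 The scheduled study duration per country includes a patient recruitment phase of up to 18 months", and individual follow-up then lasts as long as that timeframe allows. The final report is due in December 2030, one year after data collection ends. Data collection is extended only if a country's observational period is prolonged, and no prolongation is scheduled.

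Two other places depend on long follow-up. The DXA-frequency endpoint in section 9.1.2 counts patients with at least four years of treatment "who received at least 4 DXA scans between 10 months until end of study". The primary analysis in section 9.7.3.3 is limited to patients treated for more than 12 months "where z-scores of lumbar spine, total hip, or femoral neck are available".

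**The concern.** A cohort loses patients to follow-up in two ways: they drop out, or the study ends before they have been observed long enough. Table 2 allows for the first and not the second. With recruitment spread over up to 18 months and a window of at most about 48 months, late entrants cannot contribute to the later rows however well they are retained.

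The study is descriptive and its size rests on feasibility. Table 2 is therefore the only quantitative statement of what it can deliver on long-term bone density. A reader would take from it that about 400 four-year users will give an estimate to within 1.5 percentage points. If that cohort is empty or nearly so, the four-year precision does not exist and the four-year DXA endpoint has almost no denominator.

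**Working it through.** **Inputs from the protocol.** Enrolled: 1,000. Yearly dropout: 20%. Expected proportion: 2.5%, two-sided 95% interval (section 9.5). First patient: 1 January to 30 June 2026. Recruitment: up to 18 months (section 6). First dose up to 3 months before enrolment, with time points counted from treatment start (Table 1). End of data collection: about December 2029, from the December 2030 report date less one year.

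**Assumptions not in the protocol.** Uniform accrual, all countries open at first patient first visit (favourable to the plan), and dropout independent of entry date.

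**Step 1: reproduce Table 2.** N(t) = 1,000 × 0.8^(t/12) gives 800, 640, 512 and 409.6. Half-width = 1.96 × √(0.025 × 0.975 / N) gives 1.08, 1.21, 1.35 and 1.51 percentage points. These match Table 2 after rounding, so its arithmetic is correct on its own premise.

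**Step 2: the window.** January 2026 to December 2029 is W = 48 months; end of June 2026 to December 2029 is W = 42 months.

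**Step 3: share whose entry date allows t months.** f(t) = (W + L − t) / R, held between 0 and 1, where L is the lead from first dose to enrolment (0 to 3 months) and R = 18. Expected number = f(t) × N(t).

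| W | L | f(36) | n at 36 months | f(48) | n at 48 months |
|---|---|---|---|---|---|
| 48 | 0 | 12/18 | 341 (±1.66%) | 0 | 0 |
| 42 | 0 | 6/18 | 171 (±2.34%) | 0 | 0 |
| 48 | 3 | 15/18 | 427 (±1.48%) | 3/18 | 68 (±3.70%) |
| 42 | 3 | 9/18 | 256 (±1.91%) | 0 | 0 |
| Table 2 | – | 1 | 512 (±1.35%) | 1 | 409 (±1.50%) |

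If the lead is spread evenly over 0 to 3 months, the 48-month number in the longest window is about 34 (f = 1.5/18 = 0.083).

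**Step 4: 24 months.** For W = 42 and L = 0, f(24) = (42 − 24)/18 = 1, so 640 stands. The 800 at 12 months stands too.

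**Step 5: what would rescue the later rows.**
- For 409 at 48 months, f must equal 1. In the longest window with full lead, 48 + 3 − 48 = 3, so all 1,000 would have to enrol within 3 months.
- For 512 at 36 months without lead, recruitment must finish in 48 − 36 = 12 months in the longest window, or 42 − 36 = 6 months in the shorter one.
- With 12-month accrual, 48 months still gives at most 409.6 × 3/12 = 102.
- Borrowing the ±6-month window that section 9.7.3.4 gives for the exploratory density-change analysis, 48 months gives at most 409.6 × (48 + 3 − 42)/18 = 205, or 137 without lead. The same tolerance brings 36 months to 512 in the longest window and 341 to 427 in the 42-month window.

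**The case against.** Table 2 contains no computational error, and its column heading says that only annual dropout is subtracted. The recruitment phase is an upper limit, so accrual could be faster. The protocol foresees prolongation. The study tests no hypothesis, and the primary endpoint is a proportion among users treated for more than 12 months, not an estimate at 36 or 48 months. All of this is fair. It limits the severity and makes the 36-month shortfall conditional. It does not rescue 409: neither 12-month accrual nor a ±6-month tolerance gets beyond about half of it, and a prolongation that is only contingent conflicts with the December 2030 report date.

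A reader might infer four stronger points that the documents do not support.

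- **That the 24-month row fails and nobody reaches 36 months.** This needs data collection to end in July 2029. The report date places the end near December 2029.
- **That 48 months is strictly impossible.** Table 1 counts from treatment start, so a few early entrants could reach it in the longest window.
- **That precision must be shown by regimen.** The primary objective names the regimens, "200 mg (with ABT) and 100 mg (with and without ABT) dosing regimens", but section 9.7.2 makes the overall population the analysis and stratifies only where numbers allow.
- **That missing scans are concealed.** Section 9.9 says routine scanning is outside the study's control and recalls that "a high rate of missing BMD measurements at week 24 and week 52 due to study discontinuations was observed in the two pivotal studies". The protocol gives no expected scan share, so any figure would be invented. What remains is that Table 2 treats every retained patient as evaluable, which makes its numbers upper limits.

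**Conclusion.** The point holds for the calendar. Under the stated milestones the 48-month row is not achievable without prolongation: 0 patients counted from enrolment, and at most about 68 from treatment start, against 409. The at-most-68 figure rests on uniform 18-month accrual; the conclusion that 409 is out of reach does not, because it would take complete enrolment within about 3 months of the earliest possible start.

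The 36-month row is probably a partial cohort, at 171 to 341 without lead time and 256 to 427 with the full lead. This part does depend on accrual speed and lead time. The 12- and 24-month rows stand on the calendar, given simultaneous country starts; launches staggered by country could only lower the numbers.

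This should be fixed, because the protocol states a long-term precision that its schedule cannot provide. It does not invalidate the primary analysis or the enrolment target.

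**What to change.** Recompute Table 2 as enrolled × retained × share whose entry date allows that follow-up before the end of data collection, and state the accrual and lead-time assumptions. Then choose one of two routes:

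- keep the milestones, mark the 48-month row and the four-year DXA endpoint as not estimable or nearly empty, and label the 36-month row a partial cohort; or
- schedule the prolongation and move the end of data collection and the report date to match.

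Add a note that all rows are upper limits, because the primary analysis uses only patients with an available z-score. In sections 9.1 and 9.5, describe the 1,000 as patients enrolled as new users, consistent with section 9.2.2 and Table 2, rather than as long-term users.

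The first route costs some rewording and a less favourable stated precision. The second costs time. Neither needs extra patients.
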